**Table 2. Adherence and Dose Escalation Criteria**

Generic Name	Standard dosing schedule	(Presumed) day supply	Criteria for dose escalation for medication effectiveness
SC/oral only			
tofacitinib	5 mg twice daily or 11 mg once daily	Day supply rounded to the nearest 30 day period. Day supplies less than 15 days will be rounded to 30 days.	At least 1 claim in the follow-up period with an average daily dose of at least 15 mg/day for both 5 mg and 11 mg doses.

### 8.6.5. Health Care Cost and Utilization

All cost and utilization measures will be identified in the 12-month pre-index period and the 12-month post-index period. Claims occurring on the index date will be considered part of the post-index period. Baseline and follow-up costs and the change in 12-month costs from baseline to follow-up will then be examined. Cost measures will comprise the total amount paid by the health plan and patient.

- **Health care resource utilization**-Health care resource utilization will be calculated for ambulatory visits (office and outpatient), emergency department (ED) visits, and inpatient admissions.
- **RA-related resource health care utilization**-Health care resource utilization related to RA will be calculated for ambulatory visits, emergency room (ER) visits, and inpatient admissions. Utilization will be defined as RA-related if the claim had a diagnosis for RA in any position and/or is for the administration of a biologic or NB-DMARD.
- **Health care costs**-Health care costs will be computed as the combined health plan and patient paid amounts. Costs will be calculated as total costs, pharmacy costs, and medical costs. Medical costs will be further broken down into ambulatory costs, emergency services costs, inpatient costs, and other costs. Costs will be adjusted using the annual medical care component of the Consumer Price Index (CPI) to reflect inflation between 2013 (the earliest start of the pre-index period) and 2015 (the cost of claims occurring in 2016 will not be adjusted).

Costs from other payers are of importance for older patients dually eligible for commercial and Medicare coverage. Payments from Medicare (and other payers) will be estimated based on coordination of benefits information obtained by the health plan in its usual course of business. This study will incorporate the amounts estimated to be paid by other payers for a total paid or allowable amount.

[figure not shown]
- **RA-related health care costs-CPI- and coordination of benefits (COB)-adjusted** RA-related health care costs will be calculated as total costs related to RA (treatment and other medical claims with a diagnosis of RA). RA-related treatment costs will include the cost of tofacitinib, biologic DMARDs, non-biologic DMARDs, and administration of intravenous (IV) biologics (CPT = 96413 or 96415). Medical costs will include all utilization with a diagnosis of RA and are also not treatment claims. Medical costs will comprise: inpatient costs, ambulatory costs, emergency services costs, administration, and other costs.

---

 US Department of Labor, Bureau of Labor Statistics. *Consumer Price Index. Medical Care*. Series ID: CUUR0000SAM. Washington, DC: U.S. Dept. of Labor, Bureau of Labor Statistics. <http://data.bls.gov/cgi-bin/surveymost?cu>

- **Monthly costs**-Total all-cause and RA-related health care cost will be identified during each month (30-day period) of the patient’s 12-month baseline and the 12-month follow-up period.

## 8.7. Data Sources

### 8.7.1. Truven

The Truven Health MarketScan Research Databases reflects the combined healthcare service use of individuals covered by Truven Health clients (including employers, health plans, and hospitals) nationwide in the US. Truven Health builds databases comprise the healthcare experience of the clients’ covered populations, as well as information about the populations themselves and the providers that serve them. MarketScan Research Databases provide detailed cost, utilization, and outcomes data for healthcare services performed in both inpatient and outpatient settings. In the claims databases, the medical services are linked to outpatient prescription drug claims and person-level enrollment data using unique enrollee identifiers.

The MarketScan Commercial Database contains the healthcare experience of privately insured individuals. Coverage is provided under a variety of fee-for-service, fully capitated, and partially capitated health plans, including preferred provider organizations, point of service plans, indemnity plans, and health maintenance organizations.

The data that make up the Commercial Database are stored in the following tables:

- *The Inpatient Admissions Table* contains records that summarize information about a hospital admission. Truven Health constructs this table after identifying all of the service records associated with an admission (eg, the hospital claims, physician claims, surgeon claims, and claims from independent labs). Similar information (such as payments for professional services) is then summed across the claims. The admission record includes the principal procedure and diagnosis, Major Diagnostic Category, and Diagnosis-Related Group. It also includes all diagnoses and procedures (up to 14 each) found on the service records.
- *The Inpatient Services Table* contains the individual claims that are summed to create the inpatient admission records. An admission identifier on both the Inpatient Admissions and the Inpatient Services Tables identifies the claims that make up each admission record.
- *The Outpatient Services Table* comprises services that were rendered in a doctor's office, hospital outpatient facility, or other outpatient facility.
- *The Facility Header Table* contains the header records from facility claims for inpatient and outpatient services, including full diagnosis information.
- *The Outpatient Pharmaceutical Claims Table* contains outpatient prescription drug data from multiple sources, including mail-order data. Each record includes National Drug Code (NDC), therapeutic class, ingredient cost, dispensing fee, copayment, deductible, total gross payment, and other data elements.
- *The RED BOOK™ Supplement Table* contains RED BOOK variables that enhance prescription drug analyses. These variables are linked to the Outpatient Pharmaceutical Claims Table by NDC.
- *The Annual Enrollment Summary Table* provides a single record per year for each enrollee, showing enrollment start and end dates and, for some demographic variables, the most prevalent demographic and plan information; for other variables, monthly values are included.
- *The Enrollment Detail Table* provides a single record per month of enrollment for each enrollee, with detailed demographic information.
- *The Population Aggregate Table* provides average counts of the covered (insured) population to use for rate-supported analysis. The counts are recorded by several demographic variables (eg, age group, gender, region, etc.).

The MarketScan Medicare Supplemental Database contains the healthcare experience of individuals with Medicare supplemental insurance paid for by employers. Both the Medicare-covered portion of payment (represented as Coordination of Benefits Amount, or

COB) and the employer-paid portion are included in this database. The tables that make up the Medicare Supplemental Database are the same as those that make up the Commercial Database.

Claims are not included in the database until they have been adjudicated; there is a lag of approximately six months after the close of a calendar year or a quarter between services provided and their inclusion in the Research Databases. However, the Early View Database has a 90-day lag that includes paid amounts for 100 percent of prescription drugs, approximately 85 percent of physician office visits, and approximately 70 percent of hospital claims. The MarketScan Early View Database includes all of the components found in the standard MarketScan Commercial and Medicare Supplemental Databases. It includes standardized inpatient, outpatient, pharmaceutical, and health-plan enrollment data. The MarketScan Early View Database captures healthcare services incurred up to 90 days before data release and includes only adjudicated claims. However, the medical component of care for some patients will not be complete, since some claims (particularly inpatient claims) take longer to be adjudicated. Because this study is examining only comorbidities prior to and treatments during or prior to tofacitinib initiation fully adjudicated claims are not required and all available data will be used including Commercial, Medicare Supplemental, and Early View Databases.

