### 8.5. Period of Observation

All patients will be required to be continuously enrolled in the health plan for at least 24 months. Patients will have a variable length baseline period of at least 12 months. The 12 months prior to the index date will be used to assess the majority of pre-index characteristics. However, for select measures, eg, number of prior biologic therapies, and years since first RA diagnosis, the entire variable length baseline period will be utilized.

Measures utilizing the variable length baseline are noted. All baseline periods will be censored at January 1, 2012. The twelve months following the index date will be used to assess outcomes including treatment patterns, and health care costs, utilization and medication effectiveness.

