- **Compare all-cause and RA-related health care utilization among tofacitinb+MTX patients who discontinue MTX vs. persist with MTX or experience interrupted MTX.**

For this objective descriptive analysis will be conducted. Utilization measures (flags and 12-month counts) will be presented per patient during the baseline and follow-up periods. In addition, for counts the change from baseline to follow-up will be calculated.

- **Compare all-cause healthcare costs among tofacitinib+MTX patients who discontinue MTX vs. persist with MTX or experience interrupted MTX.**

For this objective descriptive and multivariable analysis will be conducted. For the descriptive analysis, 12-month cost measures will be presented per patient during the baseline and follow-up. The change in 12-month costs from the baseline to the follow-up will also be calculated. In addition, total all-cause cost will be presented in each of the months of the baseline and follow-up. The mean cost in each month will be included on a figure demonstrating the trend in costs over time. Multivariable analysis of follow-up health care cost will also be conducted using generalized linear models (see [Section 8.10.3](#)).

- **Evaluate the primary and secondary objectives in cohorts of interest.**

All objectives will be evaluated for Commercial and Medicare Supplemental lives separately as well as by Monotherapy vs. Combination regimens as identified in [Section 8.10.2](#) and by prior biologic experience (0, 1, 2, 3+ at any time prior to index).

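### Section 8.7.1 accepts incomplete Early View medical claims on a premise that omits the study's own 12-month post-index cost, utilization and effectiveness outcomes; the likely effect is small

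*Combined protocol and SAP*

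**What the plan says.** Section 8.7.1 describes two feeds. For the standard databases, "there is a lag of approximately six months after the close of a calendar year or a quarter" separates a service from its appearance in the data. Early View "captures healthcare services incurred up to 90 days before data release and includes only adjudicated claims". It has all prescription paid amounts, but only "approximately 85 percent of physician office visits, and approximately 70 percent of hospital claims". The section acknowledges that "the medical component of care for some patients will not be complete, since some claims (particularly inpatient claims) take longer to be adjudicated". It then decides to use every available source, Early View included, for this reason: "Because this study is examining only comorbidities prior to and treatments during or prior to tofacitinib initiation fully adjudicated claims are not required".

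Other sections set a wider scope. Section 8.5 states: "The twelve months following the index date will be used to assess outcomes including treatment patterns, and health care costs, utilization and medication effectiveness". Section 8.6.5 measures office, outpatient, emergency and inpatient use before and after index, and adds: "Baseline and follow-up costs and the change in 12-month costs from baseline to follow-up will then be examined". For all-cause cost, Section 8.10 states: "Multivariable analysis of follow-up health care cost will also be conducted using generalized linear models". It also plans a figure of mean cost by month. Section 8.6.4 judges one-year effectiveness partly on glucocorticoid injections and on switches to other biologics.

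Section 8.12 does not list incomplete follow-up claims as a limitation. No section states a data cut or plans a check on completeness.

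**The concern.** The reason given for tolerating incomplete medical claims does not describe this study. Even if treatments during initiation is read generously to cover on-treatment patterns, four of the five secondary objectives in Section 7 (RA-related cost, effectiveness, utilization, all-cause cost) fall outside it.

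Any loss would be one-sided. Baseline claims are old enough to be essentially complete, while the latest follow-up claims are not. That pulls follow-up medical cost and utilization down relative to baseline, affecting the planned change scores and the last points of the monthly cost figure. A missed injection (criterion 6 of Section 8.6.4) or a missed switch to an infused biologic billed by HCPCS code (criterion 3) would make a patient look more effectively treated than was the case.

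**Working it through.** The plan gives no figure for this exposure, so there is none to reproduce. The check is date arithmetic on the plan's own dates.

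**Inputs**
- Index dates: 1 Jan 2014 to 31 Jan 2017 (Section 8.2.1), which is 365 + 365 + 366 + 31 = 1,127 days.
- Follow-up: 12 months (Section 8.5), taken as 365 days including the index day. The last follow-up day is 31 Jan 2017 + 364 days = 30 Jan 2018.
- Data collection: 1 to 31 May 2018 (Section 5).
- Lags: about six months after the close of a quarter or a year for standard data; 90 days for Early View (Section 8.7.1).
- Missing share in Early View: 30% of hospital claims, 15% of office visits, 0% of prescriptions (Section 8.7.1).

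**Assumptions not in the documents:** index dates are uniform; extraction falls within the May 2018 milestones; the paid-amount percentages can be read as shares of claims; claims are spread evenly over follow-up.

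**Step 1: how far each feed reaches.** Third quarter 2017 plus six months is 31 Mar 2018, so on the quarterly reading standard data end at 30 Sep 2017. The fourth quarter, or the full year 2017, is due about 30 Jun 2018, after data collection closes. Early View reaches 31 Jan 2018 (1 May less 90 days) to 2 Mar 2018 (31 May less 90 days). Services from 1 Oct 2017 to 30 Jan 2018 are therefore in Early View only.

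**Step 2: who is exposed (quarterly reading).** Index dates from 2 Oct 2016 onward have some follow-up past 30 Sep 2017: 122 / 1,127 = 10.8% of patients. Their exposed days run from 1 to 122, so the exposed share of follow-up time is (122 × 123 / 2) / (1,127 × 365) = 7,503 / 411,355 = 1.82%.

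**Step 3: loss at the flat Early View rates.** Loss = missing share × exposed share.
- Hospital claims, average: 0.30 × 1.82% = 0.55%.
- Office visits, average: 0.15 × 1.82% = 0.27%.
- Hospital claims, month 12 of the cost figure (days 330 to 359): on average 102.5 of 1,127 index dates are exposed, 9.09%; × 0.30 = 2.7%.
- Last-indexed patient: 122 / 365 = 33.4% of follow-up; × 0.30 = 10.0% of hospital claims and × 0.15 = 5.0% of office visits.

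**Step 4: allow for claims maturing.** The flat rate treats every Early View claim as if it were 90 days old. Suppose instead that the missing share of hospital claims falls in a straight line from 30% at 90 days to zero at 182 days: 0.30 × (182 − age) / 92. On 1 May 2018 the youngest follow-up claim is 91 days old; on 31 May it is 121 days old. Hospital-claim loss is then:

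| | Extract 31 May | Extract 1 May | Flat rate (Step 3) |
|---|---|---|---|
| Average | 0.03% | 0.10% | 0.55% |
| Month 12 | 0.27% | 0.76% | 2.7% |
| Last-indexed patient | 1.7% | 3.7% | 10.0% |

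For example, the 1 May average is 0.30 × 91 × 15.5 / 411,355 = 423 / 411,355 = 0.10%.

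**Step 5: annual reading.** If standard data arrive only by calendar year, they end at 31 Dec 2016. Then 395 / 1,127 = 35% of patients and 77,745 / 411,355 = 18.9% of follow-up time are exposed; × 0.30 = 5.7% of hospital claims. This applies the 90-day shortfall to services up to about 16 months old at extraction, so it can serve only as a ceiling.

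**Step 6: what is not exposed.** Prescriptions are complete in Early View. Tofacitinib and oral MTX fills, adherence, MTX cohort assignment and pharmacy cost are therefore untouched. Section 8.6.5 counts tofacitinib and other DMARD costs in RA-related cost, so the loss on total cost is smaller than the hospital-claim loss.

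**The case against.** The strongest reply is that the effect is too small to matter. The average loss is a fraction of one percent even for the worst-affected component, and the main drug costs are complete. The objectives compare MTX cohorts, and a shortfall shared by the cohorts largely drops out of those contrasts. This stands, and it is why the point is minor.

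A second reply is that the figures are softer than they look. Section 5 gives milestones, not a data cut. The lags and completeness percentages are approximate and refer to paid amounts. Nothing supports uniform index dates: index dates weighted toward the end of the window would raise the averages, and earlier ones would lower them. This also stands. The averages and the month-12 value are scenario values, not bounds.

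Neither reply rescues the sentence in Section 8.7.1. Its premise conflicts with Sections 7, 8.5, 8.6.5 and 8.10, and no other section repairs it.

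A reader might infer that the cohort comparisons or the primary objective are compromised. The documents do not support that. The primary treatment-pattern measures are mostly pharmacy-based, and the cohort contrasts would be biased only if index dates differed by cohort, which is not shown. A reader might also take 35% of patients and 5.7% of hospital claims as the expected effect; Step 5 shows why they are a ceiling only.

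**Conclusion.** The point holds as a minor one: the justification is wrong as written, and its practical effect is probably small. On the quarterly lag with uniform index dates, about 11% of patients and 1.8% of follow-up time rest on Early View. Hospital-claim loss is roughly 0.03% to 0.5% on average, up to about 3% in month 12 of the cost figure, and up to about 10% in the last-indexed patient. The upper values assume no maturing of claims beyond 90 days.

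The direction is a small downward shift in follow-up medical cost and utilization against baseline, with possibly a few missed injections or infused-biologic switches. No rate for those events is given, so their effect on the effectiveness outcome cannot be sized. Confidence is high in the contradiction and lower in the size, because the plan states neither the data cut nor which lag applies.

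**What to change.** 1. In Section 8.7.1, delete the statement that full adjudication is unnecessary. State the data cut and whether the quarterly or the annual lag applies.
2. Keep the full sample for the main analysis, and keep Early View for pharmacy-based measures.
3. For outcomes read from medical claims, add a sensitivity analysis limited to patients whose 12 months end within the standard data: index date by about 1 Oct 2016 on the quarterly reading, or about 2 Jan 2016 on the annual.
4. Add incomplete late follow-up claims to the limitations in Section 8.12.

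Items 1, 2 and 4 are wording only. Item 3 costs one further run on about 11% fewer patients (quarterly) or 35% fewer (annual). Section 8.10.6 expects a relatively small sample, so this should not replace the main analysis.

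Optional, if the timeline allows: refresh with the standard release through 31 Dec 2017, due about 30 Jun 2018 and so ahead of the 30 Sep 2018 report. It would leave 30 / 1,127 = 2.7% of patients and 465 / 411,355 = 0.1% of follow-up time in Early View. The cost is data collection running about a month past 31 May 2018, plus rerunning the programs and the second-programmer verification of Section 8.11. The likely average loss does not require it.

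Section 8.6.5's price adjustment is silent on 2017 and January 2018 claims. That is a separate matter and should be handled on its own.

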### **8.8. Study Size**

The sample size for this study is fixed by the duration of the observation window. No formal sample size computation was performed. All patients who meet inclusion/exclusion criteria will be included in the analyses.

### **8.9. Data Management**

The MarketScan Research Databases comply with both the spirit and the letter of the Health Insurance Portability and Accountability Act of 1996 (HIPAA). The MarketScan Databases meet the criteria for a limited-use dataset and contain none of the data elements prohibited by HIPAA for limited-use datasets.

### **8.10. Data Analysis**

#### **Primary Objective**

- **To compare treatment patterns including dosing, concomitant medication use, adherence, persistence and switching** among tofacitinib+MTX patients who discontinue MTX vs. persist with MTX or experience interrupted MTX.

For this objective, treatment patterns will be summarized across the cohorts of interest. Specific treatment patterns include non-persistence with the index medication, receipt of an opioid, receipt of an NSAID, adherence with the index medication, adherence with MTX.

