#### **8.10.1. Descriptive Analysis**

All study variables, including pre- and post-index measures, will initially be analyzed descriptively. In general, numbers and percents will be provided for dichotomous and polytomous variables, while means, medians, and standard deviations will be provided for continuous variables. Missing or unavailable data will not be imputed.

Results will be stratified by treatment cohort, bivariate comparisons of pre- and post-index measures will be provided, and appropriate tests (eg, t-test, Mann Whitney-U test, chi-square test) will be used based on the distribution of the measure. The analysis that is performed (ie, the methods that are used and the patients who are included) will be specific the objective being examined. Descriptive techniques will be implemented for each objective.

Multivariable techniques (including effect decomposition) will be used when comparing outcomes and controlling for differences in patient characteristics between study cohorts.

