#### **8.10.2. Multivariate Analysis**

To control for possible confounding of the relationship between the outcomes and independent variable of interest, select objectives will be conducted utilizing multivariable methods as described above.

Final outcomes for multivariate analysis will be selected after review of descriptive results. Possible outcomes of interest include: total all-cause health care cost, total RA-related health care cost, cost of biologics/tofacitinib/administration/nb-DMARDs, medication effectiveness (yes vs. no).

For each model, specific predictors to be included will be determined based upon clinical rationale and statistical significance. Variables listed in [Section 8.6.1](#) and [8.6.2](#) will be considered for inclusion in the multivariable models. Additional variables identified throughout the course of the study will also be considered. Following standard procedure,

regression diagnostics will be performed for each model to assess goodness of fit and violations of model assumptions (eg, multicollinearity, heteroskedasticity). When there are violations of the model, programmers will note them and make appropriate corrections to the data (ie, typically through transformation of either the independent or dependent variables) or in the method of estimation.

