### **8.10.6. Decomposition**

Given that the sample size for this study will be relatively small and the comparator populations will be noticeably different, implementing propensity score matching may reduce the available sample below what is needed for a meaningful study. One possible solution would be to implement a method known as decomposition [Blinder (1973), Oaxaca (1973)] Decomposition splits out the treatment effect into two parts, the effect of the actual treatment and the effect of the other differences between the treatment groups. Presumably, if the treatment groups were randomly assigned, then the effect of the treatment would be the entire effect and the effect of all other differences would be negligible. However, since biologic treatment choice is not randomly assigned, the decomposition method would determine how much of the treatment effect is due to the medication and how much is due to the difference in characteristics between the two tofacitinib cohorts (tofacitinib+MTX patients who withdraw MTX or continue MTX).

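### The primary comparison of MTX cohorts is assigned no adjusted analysis although the plan expects noticeably different cohorts, and its sections disagree on which adjusted analyses will be run

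*Combined protocol and SAP*

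**What the plan says.** Section 7 sets a primary objective of comparing dosing, concomitant medication, adherence, persistence and switching between patients who withdraw MTX and those who persist with it or interrupt it. For the analysis, Section 8.10 says "For this objective, treatment patterns will be summarized across the cohorts of interest" and names no model. Section 8.10.1 covers all study variables and states that "bivariate comparisons of pre- and post-index measures will be provided", with t, Mann-Whitney or chi-square tests.

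On adjustment:

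- Section 8.10.1: "Multivariable techniques (including effect decomposition) will be used when comparing outcomes".
- Section 8.10.2: "select objectives will be conducted utilizing multivariable methods as described above", and "Final outcomes for multivariate analysis will be selected after review of descriptive results". Its candidate outcomes are three cost measures and medication effectiveness.
- Section 8.10, secondary objectives: both cost objectives are committed to generalized linear models under 8.10.3. Effectiveness is first said to receive multivariable analysis and then said possibly to receive it. Utilization is descriptive.
- Section 8.10.6: because the sample is small and "the comparator populations will be noticeably different", matching may not be feasible. "One possible solution would be to implement a method known as decomposition".

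Section 8.10.2 draws predictors from 8.6.1 and 8.6.2, plus variables found during the study, and chooses among them partly by statistical significance. Section 8.6.2 contains post-index as well as pre-index corticosteroid, opioid and NSAID use.

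**The concern.** Patients who stop MTX may differ at baseline from those who stay on it, and the plan itself expects the groups to differ. A team that follows Section 8.10 literally can report the primary comparison with unadjusted tests only. A difference in tofacitinib persistence or opioid use could then reflect baseline severity, comorbidity or steroid use, all of which the study already derives.

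Two further problems follow from the wording. Whether a listed outcome is modelled, and whether decomposition is run, can be decided after the descriptive results are known. And nothing stops a post-index measure from entering a model. Post-index oral steroid use feeds effectiveness criterion 5 in Section 8.6.4, and opioid and NSAID receipt are themselves primary outcomes. Adjusting for such measures could remove or distort part of a real difference.

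**Working it through.** The plan gives no sample size, power or effect size (Section 8.8), so there is no figure to reproduce. The main check is of the text.

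**Which objectives are sent to a model section?** In Section 8.10, the RA-related and all-cause cost objectives point to 8.10.3 and effectiveness points to 8.10.4. The primary objective points to none. Sections 8.10.4 and 8.10.5 say how binary and continuous variables are modelled, but name no primary outcome.

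**Do the statements agree?**

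1. Scope. Section 8.10.1 applies multivariable techniques when outcomes are compared. Section 8.10.2 limits them to selected objectives, and Section 8.10 gives treatment patterns and utilization descriptive analysis only.
2. Cost. Section 8.10 commits to the cost models. Section 8.10.2 calls the same outcomes possible and selects after the descriptive results.
3. Effectiveness. Section 8.10 says *will*, then *may*.
4. Decomposition. It is firm in 8.10.1 and a possibility in 8.10.6.

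**How large could the confounding be?** Every input here is assumed. Take one binary factor with prevalence p1 and p0 in two cohorts that multiplies the risk of non-persistence by k, with no true cohort effect:

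crude RR = [1 + p1(k − 1)] / [1 + p0(k − 1)]

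With a risk of 35% in the comparison cohort:

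| p1 | p0 | k | Crude RR | 35% appears as |
|---|---|---|---|---|
| 0.5 | 0.4 | 1.5 | 1.25/1.20 = 1.04 | 36.5% |
| 0.5 | 0.4 | 2.0 | 1.50/1.40 = 1.07 | 37.5% |
| 0.5 | 0.3 | 1.5 | 1.25/1.15 = 1.09 | 38.0% |
| 0.5 | 0.3 | 2.0 | 1.50/1.30 = 1.15 | 40.4% |

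The spurious difference is 1.5 to 5.4 points. Its standard error is √[0.35 × 0.65/n + q(1 − q)/n], where q is the risk in the last column. This is about 9.6–9.7 points at n = 50 per cohort and 6.8 points at n = 100. The rejection rate of a nominal 5% two-sided test is P(Z > 1.96 − d/SE) + P(Z < −1.96 − d/SE), where d is the spurious difference. It is 5.3% for d = 1.5 at n = 50 and 12.3% for d = 5.4 at n = 100. A wider imbalance of 60% versus 30% with k = 2.0 gives RR 1.60/1.30 = 1.23.

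**Can the sample carry adjustment?** A set with cohort (2 parameters), age, sex, severity, comorbidity, prior biologic count and baseline corticosteroid use (1 each) has 2 + 6 = 8 parameters, or 9 with baseline use of the same drug. At an assumed 10 events per parameter, 8 parameters need 80 events. An assumed 150–300 patients with 30–50% non-persistent give 150 × 0.30 = 45, 150 × 0.50 = 75, 300 × 0.30 = 90 or 300 × 0.50 = 150 events. The full set fits in two of these four cases, so a reduction rule is needed.

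**The case against.** The best defence is that the general sentence in 8.10.1, read with the generic models in 8.10.4 and 8.10.5, already covers outcomes such as non-persistence, and that the list in 8.10.2 is not exhaustive. This stands as far as permission goes: the plan allows such models. It does not require them, and on this reading 8.10.1 contradicts both the limit in 8.10.2 and the descriptive-only utilization objective.

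A second defence is that, in a small study without a power calculation, a descriptive primary analysis with adjusted secondary outcomes is reasonable. It can be, if stated. Here the objective is to compare, and significance tests are attached.

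Third, Section 8.10 stratifies by insurance type and prior biologic count, and Section 8.4 lists prior MTX as a subset for some outcomes. That helps in part, but does not address severity, comorbidity or steroid use.

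Fourth, cohorts are defined by MTX behaviour over the same 12 months as the outcomes (Sections 8.3 and 8.5). That bias may exceed the confounding illustrated here, and adjustment does not remove it. This stands and limits what the fix can achieve. It does not justify leaving measured baseline differences unaddressed.

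A reader might also see a contradiction in the reference in 8.10.6 to "the difference in characteristics between the two tofacitinib cohorts", since Section 8.3 defines three. The documents do not clearly support that: Section 8.3 allows the discontinued and interrupted cohorts to be combined if the sample is insufficient. What is missing is a statement of which contrast a decomposition would use.

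**Conclusion.** The point holds on the text. No section assigns an adjusted analysis to a primary outcome, the plan expects dissimilar cohorts, and its statements on cost models, effectiveness models and decomposition cannot all be followed. The plan should be changed.

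The numerical size is unknown. The risk ratios of 1.04–1.15 rest on an assumed single confounder, and at the low end the rejection rate of 5.3% is hardly above nominal.

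Three stronger readings are not supported. The plan does not lack adjustment altogether; the gap is specific to the primary objective. It does not say that post-index measures will be covariates: Section 8.10.2 only puts 8.6.2 variables up for consideration, with clinical rationale as one criterion, so the fault is a missing exclusion. And it does not let outcomes go unreported, because 8.10.1 has all study variables analysed descriptively; what is left open is which of them are modelled.

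**What to change.** 1. **Section 8.10, primary objective.** Keep the unadjusted table. Beside it, add adjusted models in the full sample: logistic (8.10.4) for tofacitinib non-persistence, switching, opioid receipt and NSAID receipt, and linear (8.10.5) for tofacitinib proportion of days covered. Keep dosing and MTX adherence descriptive; MTX adherence largely follows from the cohort definition.
2. **Sections 8.10, 8.10.1, 8.10.2 and 8.10.6.** Replace selection after the descriptive results with a statement that all listed outcomes will be modelled and reported. Change *may* to *will* for effectiveness. Say which outcomes the general sentence in 8.10.1 covers. State whether decomposition is run and, given the merging rule in 8.3, for which cohort contrast.
3. **Covariates, Section 8.10.2.** Allow only pre-index measures, drop the significance screen, and fix a short, clinically chosen set before results are seen. Enter age and sex as their own terms alongside severity, comorbidity, prior biologic use and baseline corticosteroid use. Add baseline use of the same drug in the opioid and NSAID models. State in advance a reduced set or penalised estimation for use when events are too few.

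The cost is wording changes and about five more models on variables already derived. Estimates will be imprecise in a small sample, particularly for rarer outcomes such as switching. Reporting every listed model removes the choice among outcomes but does not control multiplicity. Because the cohorts are defined over the outcome period, report adjusted results as associations.
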